##### 4.4.1. Preparation phase:

This phase includes writing the project, obtaining approval from the ethics committee of the University of Burgos, registering it on the Clinicaltrials.gov platform, as well as beginning to collect the sample.

It will run during the months of June-July and the first week of September 2023.

As the sample is obtained, it will be randomized and assigned to the different groups.

#### 4.4.3. Analysis and Reporting

This phase will take place between the final weeks of December 2023 and throughout January-February 2024.

#### **4.5. Evaluation instruments**

The following evaluation tools are proposed:

##### 4.5.1. Nine Hole Peg Test:

This test is included to assess manual dexterity.

The Nine Hole Peg Test (NHPT) (Mathiowetz et al, 1985) consists of a manual test, in which the subject must place 9 pegs in their corresponding 9 holes, and remove them again, the measured variable being the time It takes time to complete the entire process.

##### 4.5.2. Box and Block: The

Box and Block test is a tool with standardized dimensions and materials.

It is specified that the subject must sit in front of a rectangular box with his hands next to it. This box is made of wood with a base 53.7 cm wide and 25.4 cm long; This is divided into two square compartments with a side of 25.4 cm each, separated from each other by a 15.2 cm high divider; Both compartments are padded in order to reduce noise during testing. The test contains 150 cubic-shaped wooden blocks measuring 2.5 cm on each side. The number of blocks that the subject has transported from one compartment to another with each hand in one minute of time must be recorded.

Higher scores indicate better manipulative skill.

#### 4.5.3 Jamar hand dynamometer

The Jamar hand dynamometer is used to measure grip strength in the hand, it allows the force exerted by the individual to be converted into a numerical reading. The subject is asked to grasp the device and is instructed to perform the maximum sustained contraction. The force is recorded in kilograms.

#### 4.5.2 Chronometry:

The evaluation of motor imagination capacity requires at least two tests.

Chronometry is defined as the temporal congruence between an executed motor act and the same imagined act.

In this case, the NHPT itself is proposed as the motor act executed. So once administered to obtain the test's own variable (time taken to perform), the participant will be asked to imagine performing the test, and it will be timed. Both measurements will be taken in seconds, to calculate the chronometric ratio, according to the formula (Liepert, 2012):

$$Rc = \frac{\text{(Time executed motor act – Time imagined motor act)}}{\text{Time motor act performed}}$$

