#### 1.- Introduction/Justification

Motor imagination (MI) is defined as the cognitive process of imagining the movement of a part of a person's own body without actually moving that part of the body (Al-Saegh et al.,2021).

IM training in healthy adults has been shown to improve strength, arm positioning speed, and joint range (Dickstein and Deutsch, 2007). On the other hand, the capacity of MI has been shown to be related to proprioception. Shenton et al (2004) have suggested that proprioception, in some circumstances, may represent an important input at the sensory level that contributes to the representation of the body; Furthermore, McCormick et al (2007) have suggested that altered proprioceptive input could alter MI tasks.

The research question of this work is based on seeing if the relationship between IM and the aforementioned parameters also occurs the other way around. Could improving strength and/or manual dexterity also improve IM?

Neuromuscular electrical stimulation (NMES) is an application of electrical stimulation used in movement rehabilitation Stein et al

(1992). Functional electrical stimulation ( *FES*) is a subtype of NMES in which stimulation supports functional and purposeful movements Popovic et al (2001). This technique consists of applying electrical currents to the muscles, making them contract in a sequence that allows you to perform different tasks. Some of the examples are: holding a key, holding a toothbrush, standing or walking Vodovnik et al (1978).

The technology was developed in the 1960s, during which initial clinical use began, emphasizing its potential as an assistive device Hoshimiya et al (1989). Since then, FES has evolved into an important therapeutic intervention that rehabilitators can use to help people with diseases or injuries to the nervous system regain their ability to stand, walk, reach and grasp Buckett et al (1988) , having demonstrated positive effects in

increased muscle strength, remission of osteopenia and improved walking (Bélanger et al, 2000; Sabut, 2011).

FES device technology has traditionally been based on conventional electrodes. However, multi-field surface electrodes have emerged, consisting of groups of several small conductive fields, which can be activated/deactivated and configured independently (FesiaGrasp, 2022).

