The Fesia Grasp system is a FES-based neurological hand rehabilitation device developed by Fesia Technology (Donostia-San Sebastián, Spain). This is a commercial device designed for manual dexterity rehabilitation, which delivers a train of biphasic pulses of different widths and amplitudes to different electrode fields asynchronously, meaning that different electrode fields are activated with an interval predefined between pulses Malešević et al (2017).

Fesia Grasp, generates superficial electrical stimulation of the forearm muscles to trigger eight different flexion and extension movements of the wrist and fingers in order to restore the function, freedom and independence of the patient's hand after a stroke, Martin -Odriozola et al (2021).

The study aims to answer the PICO research question:

Q: healthy adults

I: FES and, multfield FES.

C: video games

O: Motor imagination, strength, manual dexterity.

The aim is to compare different tools in a population sector to check if there is an improvement in motor skills through the use of FES.

2.- Objectives

General objective:
 
 
• Check the effects of FES and virtual reality regarding motor imagination, strength and manual dexterity.
 
 
Secondary objectives:
 
 
• Find out if functional electrical stimulation improves motor imagination, both kinesthetic and visual, as well as manual dexterity and strength.
 
• Find out if an intervention based on the use of virtual reality improves motor imagination, both kinesthetic and visual, as well as manual dexterity.
 
• Check if there are differences between FES, multi-field FES, and virtual reality in terms of visual motor imagination, kinesthetic and manual dexterity.
 

3.- Project description

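### The chronometric ratio is built on the same Nine Hole Peg time that serves as the dexterity outcome, so a dexterity or practice gain that imagined time does not fully follow can be read as a change in motor imagery

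*Combined protocol and SAP*

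**What the plan says.** Section 4.5.1 gives the NHPT, scored as completion time, one purpose: "This test is included to assess manual dexterity". Section 4.5.2 (Chronometry) then uses the same test a second time: "In this case, the NHPT itself is proposed as the motor act executed". Both variables come from one administration: "So once administered to obtain the test's own variable (time taken to perform), the participant will be asked to imagine performing the test". The numerator of the ratio is "Time executed motor act – Time imagined motor act" and the denominator is "Time motor act performed", so the dexterity score enters twice. The section describes the construct as relative to execution: "Chronometry is defined as the temporal congruence between an executed motor act and the same imagined act".

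The Introduction lists imagery and dexterity as separate outcomes ("O: Motor imagination, strength, manual dexterity") and asks "Could improving strength and/or manual dexterity also improve IM".

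Section 3 plans comparisons between groups before training, after it and at follow-up. It also plans within-group analyses of whether training improved imagery and dexterity. Section 10 repeats the within-group and between-group plan in general terms. Neither section mentions a separate analysis of imagined time, any account of executed time when Rc is interpreted, or which direction of Rc counts as improvement.

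**The concern.** Training is intended to shorten the NHPT time. That time is the yardstick for one of only two imagery measures, so success on dexterity can move the imagery measure without any separate change in how long the participant takes to imagine the task. Rc alone cannot show whether the executed time, the imagined time or both have moved.

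What is at stake is the trial's main inference. If one arm becomes faster on the pegs and its imagined time lags behind, the difference in Rc could be published as an effect of the device on motor imagery. Within each arm, including the untreated control, repeating the NHPT at three assessments could produce the same shift through practice. Taking the absolute value of Rc does not help, because the executed time is still in it.

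**Working it through.** **Inputs from the documents.** The formula in section 4.5.2 (Chronometry), and 20–25 participants per group (section 4.3.2). The documents give no NHPT times, no SD and no value of Rc, so there is no plan figure to reproduce. All times, gains and SDs below are assumptions.

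**Algebra.** Let E be executed time and I imagined time.

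- Rc = (E − I)/E = 1 − I/E.
- Let E fall by a fraction g, and let I follow a share t of that gain: E₁ = E₀(1 − g) and I₁ = I₀(1 − t·g).
- Change in Rc = −(I₀/E₀) × g(1 − t)/(1 − g).
- The change is zero when t = 1 (full tracking) and largest when t = 0 (imagined time unchanged).

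**Worked values.** Assume E goes from 18.0 to 16.2 s (g = 0.10).

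| Baseline I | Rc before | Rc after, I unchanged | Rc after, I follows half | Rc after, I follows fully |
|---|---|---|---|---|
| 15 s | 1 − 15/18 = 0.167 | 1 − 15/16.2 = 0.074 | 1 − 14.25/16.2 = 0.120 | 1 − 13.5/16.2 = 0.167 |
| 18 s | 1 − 18/18 = 0 | 1 − 18/16.2 = −0.111 | 1 − 17.1/16.2 = −0.056 | 1 − 16.2/16.2 = 0 |
| 20 s | 1 − 20/18 = −0.111 | 1 − 20/16.2 = −0.235 | 1 − 19/16.2 = −0.173 | 1 − 18/16.2 = −0.111 |

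With incomplete tracking the signed ratio always moves down. A participant who starts at 15 s moves closer to zero and looks more congruent; one who starts at 18 or 20 s moves away and looks less congruent. The gain in peg speed is the same in all three rows.

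**Range over the gain.** With I unchanged and I₀/E₀ between 0.8 and 1.2, the shift is:

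- −0.042 to −0.063 for a 5% gain;
- −0.089 to −0.133 for a 10% gain;
- −0.141 to −0.212 for a 15% gain.

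If I follows half of a 10% gain, the shift is −0.044 to −0.067.

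**Could it reach significance at this sample size?** Assume a 10% gain in one arm only, I unchanged, I₀/E₀ = 1 (shift 0.111) and two-sided alpha 0.05. For an SD of change in Rc of 0.10, 0.15, 0.20 or 0.30, the chance of a significant between-arm difference is about 0.94, 0.65, 0.42 or 0.22 at 20 per group. For a 5% gain (shift 0.053, close to the half-tracking case above), the corresponding figures are 0.38, 0.20, 0.13 and 0.08. These show that a spurious finding is possible. They do not predict one.

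**Within or between arms.** If every arm has the same practice gain, the same tracking and a similar I₀/E₀, the shift is the same in each arm. It then drops out of the between-arm difference but stays in each within-group change. A gain confined to one arm stays in both.

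**The case against.** The strongest reply is that congruence must be measured against execution. If a participant speeds up and the imagined act does not keep pace, congruence as section 4.5.2 defines it really has changed, and calling that an artefact equates imagery with raw imagined duration. This stands: the protocol does not define imagery that way, and imagined seconds alone have no stated better or worse direction.

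A reader might infer that an arm which only becomes faster on the pegs is bound to differ from control on Rc. The documents do not support this. The participant imagines the task after performing it, so imagined time may well follow. With full tracking (E 18 to 16.2 s, I 15 to 13.5 s), Rc stays at 0.167. Nothing in the documents indicates how much tracking to expect.

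Other parts of the reply also stand. Practice common to all arms largely cancels between arms. The MIQ-RS does not use peg time, and Box and Block is a second dexterity measure. Although the Introduction asks whether dexterity improves imagery, the objectives and section 10 plan no correlation or mediation analysis that the shared term could distort. A 10% arm-specific gain in healthy adults after five 30-minute sessions is an assumption.

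The reply does not show that Rc can be interpreted without its two components. Section 4.5.2 calls for at least two imagery tests, and chronometry is one of the only two planned.

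**Conclusion.** The concern holds conditionally. One NHPT time is both the dexterity outcome and the reference for Rc, so a speed gain that imagined time does not fully follow shifts Rc, and the plan provides nothing that would reveal the source of the shift. In the assumed example with imagined time starting at 18 s, the shift is −0.111 with no tracking, −0.056 with half tracking and zero with full tracking. An arm-specific gain can affect both planned types of comparison; a common practice gain affects mainly the within-group ones.

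The documents do not support reading chronometry as invalid, or a difference in Rc as inevitable. Size and direction depend on the amount of tracking, the baseline ratio and the gain, none of which the documents give. The defect is that Rc is planned without the companion analyses needed to interpret it.

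**What to change.** In sections 4.5.2 (Chronometry) and 10:

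- Analyse executed time and imagined time, both on the log scale, alongside Rc by arm and visit, with the same within-group and between-group comparisons. The log scale suits this because log(1 − Rc) = log(imagined) − log(executed), so a change in the ratio splits exactly into its two parts.
- State that Rc measures congruence relative to execution. State also that a change in Rc accompanied by a change in executed time will not, on its own, be reported as an improvement in motor imagery, but will be interpreted with both component times and the MIQ-RS.

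A mechanical rule that accepts an imagery effect only when imagined time also differs between arms is not advised. With half tracking (imagined 18 to 17.1 s, Rc 0 to −0.056) imagined time does differ, so the rule could still label a shift driven by dexterity as imagery.

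The cost is small: both times are already recorded, and no test, visit or participant is added. The downside is two more analysed variables and a more cautious claim from chronometry.

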
The present work is a clinical, randomized study of parallel groups of a quasi-experimental type.
 
A sample of university students will be divided into 4 groups, where one of them will act as a control group (without intervention), and the other three will perform hand training with two different types of FES devices (conventional and multi-field). and a last group will receive hands-on training with video games.
 
Intergroup analyzes will be performed before the start of training (pre-intervention), after finishing the program (post-intervention), and three weeks after finishing (follow-up evaluation). Likewise, intragroup analyzes will be carried out to check whether the training has caused an improvement in the quality of motor imagination, as well as an improvement in manual dexterity in each of the groups.
 
To carry out the project, a collaboration agreement will be signed with the company FESIA TECHNOLOGY SL, which will provide a FESIA GRASP device for the study, as well as the consumables (electrodes) necessary for the development of the study. The agreement is currently being evaluated by the UBU legal office.
 
It is planned to register the study on the international platform Clinicaltrials.gov.

4.- Material and methods

4.1 Type of study
 
Controlled, randomized, parallel group clinical trial. Unicentric, and with blind evaluation by third parties. Quasi-experimental.
 
4.2. Description of devices
 
Four parallel groups are planned. A first group that will have an intervention based on multi-field FES with the FESIA GRASP device; another group that will receive only FES

with the Globus Elite electrostimulation device (device with conventional electrodes); a third group that will receive an intervention based on virtual reality; and finally a control group, which will not receive any treatment.

The three devices are described below.

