#### 10.- Description of the data analysis and the statistical study required, if applicable

The characteristics between groups will be analyzed before the start to confirm that there are no differences between them before the start of the intervention.

Subsequently, intra-group analysis will be done to see the effects on each of them, as well as inter-group analysis to see if there are differences between the different interventions. These intra-group and inter-group analyzes will be done with respect to the baseline and follow-up measurement.

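### Chronometry is defined as congruence, where 0 is best, but is scored as a signed ratio with no stated direction of improvement, so comparing it as printed can miss a gain in congruence or register a shift that leaves congruence unchanged

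*Combined protocol and SAP*

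**What the plan says.** Section 4.5.2 Chronometry states the construct first: "Chronometry is defined as the temporal congruence between an executed motor act and the same imagined act". The executed act is the Nine Hole Peg Test. The participant then imagines doing the same test and is timed. "Both measurements will be taken in seconds, to calculate the chronometric ratio", whose numerator is printed as "Time executed motor act – Time imagined motor act" and whose denominator is the executed time. No best value, direction of improvement or absolute value follows.

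Section 3 states what the analysis is meant to show: "intragroup analyzes will be carried out to check whether the training has caused an improvement in the quality of motor imagination". Section 10 describes the analysis only in general terms: "These intra-group and inter-group analyzes will be done with respect to the baseline and follow-up measurement". It does not mention Rc, and it names no test, summary statistic or transformation for any outcome.

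The general objective in section 2 covers motor imagination: "Check the effects of FES and virtual reality regarding motor imagination, strength and manual dexterity". Section 4.5.2 Chronometry adds that assessing imagery capacity takes at least two tests. Rc is the timed one and the MIQ-RS is the questionnaire.

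**The concern.** For the other outcomes in section 4.5, a reader can tell which change is an improvement. Box and Block and the MIQ-RS say that higher is better. The peg test ("the measured variable being the time It takes time to complete the entire process") and grip strength ("The force is recorded in kilograms") give no direction, but their scales run one way. Rc is the exception. Its best value lies inside its range, so neither a rise nor a fall means improvement in itself: a fall is a gain for someone above 0 and a loss for someone below 0.

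A group mean of signed Rc therefore measures the average direction of the timing error, while the stated construct is the size of that error. The two can disagree. If the choice between them is left until the data are in, it becomes a post hoc choice between scores that can give different answers about motor imagination.

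**Working it through.** **Is there a figure to reproduce?** No. The documents give no value, SD, effect size or power for Rc. The only usable input is the expected group size of 20–25 (section 4.3.2). The times and distributions below are assumptions.

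**Formulas.** With executed time E and imagined time I: Rc = (E − I)/E and |Rc| = |E − I|/E. That 0 is best is not printed. It follows from the definition, since I = E gives Rc = 0.

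**1. Equal incongruence takes opposite signs.** With E = 20 s:
- I = 14 s: (20 − 14)/20 = +0.30
- I = 20 s: 0
- I = 26 s: (20 − 26)/20 = −0.30

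**2. A gain that cancels.** One person moves from 14 to 18 s (+0.30 to +0.10) and another from 26 to 22 s (−0.30 to −0.10).
- Mean Rc: (0.30 − 0.30)/2 = 0 before; (0.10 − 0.10)/2 = 0 after.
- Mean |Rc|: 0.30 before; 0.10 after.

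**3. A shift across zero.** One person moves from 18 to 22 s. Rc goes from +0.10 to −0.10, a change of −0.20, while |Rc| is 0.10 at both visits.

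**4. The denominator is itself an outcome.** Peg test time falls from 20 to 18 s and imagined time is fixed.
- I = 16 s: Rc goes from +0.20 to (18 − 16)/18 = +0.11.
- I = 24 s: Rc goes from −0.20 to (18 − 24)/18 = −0.33.

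Signed Rc falls in both cases, but congruence improves in the first and worsens in the second.

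**5. Possible size, by simulation.** Assumptions: true Rc normal; one intervention arm against an unchanged control; n = 20–25 per arm; independent measurement noise at baseline and post-intervention; comparison adjusted for baseline; two-sided 5%; no multiplicity adjustment. Entries are approximate rejection rates, and ranges cover both group sizes and repeated runs.

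| Scenario | Noise SD | Signed Rc | Absolute Rc |
|---|---|---|---|
| Deviations halved, baseline mean 0, SD 0.25 | 0.08 | 5–6% | 85–93% |
| Same | 0.15 | 5–6% | 39–50% |
| Same | 0.20 | 5–6% | 23–28% |
| Deviations halved, baseline mean +0.30, SD 0.25 | 0.08 | 98–99% | over 99% |
| Mean shifts from +0.05 to −0.05, SD 0.15 | 0.08 | 82–91% | 5% |
| Uniform shift of 0.10 towards 0 from mean +0.30, SD 0.15 | 0.08 | 81–89% | 73–83% |
| Same shift, SD 0.25 | 0.08 | 76–88% | 45–56% |

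In the row that crosses zero, mean |Rc| is the same at both visits. For a normal variable with mean m and SD s it equals s√(2/π)·exp(−m²/2s²) + m[1 − 2Φ(−m/s)]. With m = ±0.05 and s = 0.15 this gives 0.126. Signed Rc still rejects in most trials.

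In the last two rows the share starting below 0 is Φ(−0.30/0.15) = 2% and Φ(−0.30/0.25) = 12%. There the signed score is the more powerful one.

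**The case against.** Several points on the other side have weight.

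- **Signed Rc is not wrong about what it measures.** A reader might infer that it would show a change where nothing changed. That is too strong. In a move from +0.10 to −0.10 the imagined time does change relative to the executed time, and signed Rc reports it correctly. Only congruence is unchanged.
- **The plan never says that signed Rc will be averaged or tested.** Section 10 names no scoring for any outcome, and an analyst could take absolute values without contradicting the text. This stands: comparing Rc as printed is an inference. But leaving either score open is itself the gap.
- **The formula is taken from a cited study.** That source cannot be consulted here, and absolute-value bars could have been lost when the text was extracted, though nothing shows that they were. Even so, no direction of improvement appears anywhere in the plan.
- **If nearly everyone errs on the same side, signed Rc tracks congruence and can be more powerful.** True, as the last two rows of the table show. The plan neither states nor supports that pattern, and a direction would still have to be declared.
- **|Rc| is not the only possible score.** Rc cannot exceed 1 but has no lower bound: halving the imagined time gives |Rc| = 0.5, doubling it gives 1.0. This stands as a limitation of |Rc|.

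**Conclusion.** The point holds as a mismatch between construct and score. Confidence is high that the scoring gap exists; its size is not known. The cancellation and the shift across zero follow from the printed formula by arithmetic and need no assumption about how Rc is distributed.

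The simulated rates do rest on assumptions, and noise matters most. In the scenario where the signed score does worst (baseline mean 0), the power of |Rc| ranges from about 85–93% down to 23–28% as the noise SD goes from 0.08 to 0.20. The benefit of folding may therefore be large, small or, where errors are one-sided and shift uniformly, negative for power.

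A reader might also infer that the trial's conclusions on motor imagination are unsafe as a whole. The documents do not support that. No outcome is named primary. The secondary objectives name kinesthetic and visual imagination, which are the MIQ-RS subscales, so Rc bears on the general objective only. Both times are recorded, so |Rc| can be recovered. This is worth fixing before analysis, at the lower end of importance.

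**What to change.** **Section 4.5.2 Chronometry.** State that Rc = 0 is perfect congruence, and that the analysed congruence score is |Rc| = |executed − imagined|/executed, with lower values better.

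**Section 10.** Use |Rc| for both the intra-group and the inter-group comparisons, at post-intervention and at follow-up. Between groups, include baseline |Rc| as a covariate. Use a method that tolerates skew at 20–25 per group; a permutation test is one option, not a requirement. A plain percentile bootstrap is less suitable, since it rejected in 6–7% of simulated trials with no effect.

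**Reporting.** Give signed Rc descriptively, to show the direction of error. Give executed and imagined times separately by arm and visit, because peg test time is both a dexterity outcome and the denominator, and a faster test with unchanged imagined time moves Rc and |Rc| alike.

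**Cost.** A few lines of text and no new data. The price is a skewed outcome and some loss of power if nearly all participants err on the same side and shift uniformly.
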